5.5.3.1 Adverse events

All AEs recorded during the study will be summarized. The incidence of treatment-emergent AEs (new or worsening from baseline) will be summarized by system organ class, severity (based on CTCAE grades), type of AE, relation to the study drug. Deaths reportable as SAEs and non-fatal serious adverse events will be listed by patient and tabulated by type of AE.

Treatment-emergent adverse events (TEAEs) will include all adverse events who started between first and 28 days after the last administration of study medication.

5.5.3.2 Laboratory abnormalities

All laboratory values will be converted into SI units and the severity grade calculated using appropriate Common Toxicity Criteria (CTC).

Frequency of laboratory abnormalities will be displayed by parameter and study day. Notably abnormal laboratory values (new or worsening from baseline based on CTC grades) will be summarized by laboratory parameter. Shift tables will be presented comparing baseline laboratory result (CTC grade) with the worst result (expressed in CTC grade) during study. Patient with abnormal laboratory values will be listed and values outside the normal ranges will be flagged. A separate listing of laboratory abnormalities of CTC grade 3 or 4 will also be provided.

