#### Safety Follow-up

All patients in the main and extension phases will be followed for safety for approximately 56  $(\pm 3)$  days after administration of their last dose of pasireotide LAR.

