#### 6.4.1 Follow-up for dose-limiting toxicities

Patients whose treatment is interrupted or permanently discontinued due to an AE or abnormal laboratory value must be followed up at least once a week for 4 weeks, and in 4-week intervals thereafter, until resolution or stabilization of the event, whichever occurs first. All patients will be followed up for AEs and serious adverse events (SAEs) for 8 weeks after administration of the last dose of pasireotide LAR (refer to Section 6.4.4 for information on the discontinuation of the study drug).

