# 8 Safety monitoring

# 8.1 Serious adverse event reporting

In order to ensure patient safety, each SAE, **regardless of the suspected causality**, occurring after the beginning of any period in which the study protocol interferes with the standard medical care given to the patient (for example, withdrawal of treatment during washout period, change in treatment for a fixed dose of concurrent drug) and up to 56 days after the patient receives the last IM LAR injection of the study drug must be reported to Novartis within 24 hours after acknowledgement. Any SAE experienced after this period must be reported to Novartis if the investigator suspects that there is a causal relationship to the study drug. Recurrent episodes, complications, or progression of the initial SAE must be reported as a follow-up to the original episode within 24 hours of receipt of the follow-up information by the investigator. A SAE occurring in a different timepoint or considered as not otherwise related to a previously reported event, must be reported separately as a new event.

The information about all SAEs is collected and recorded in the Serious Adverse Event Report Form. The investigator must evaluate and register the relationship between each SAE and each specific study drug (if there is more than one study drug), complete the SAE Report Form in English, and fax it, completed and signed, within 24 hours to the Novartis Integrated Medical Safety (IMS) Oncology Department.

The site-specific phone and fax numbers of the contact people at the local IMS department are indicated in the investigator's binder provided to each site. The original copy of the SAE Report Form and the fax confirmation page must be kept together with the documentation of the case report form at the study site.

Follow-up information is submitted to the same person as the original SAE Report Form, using a new SAE Report Form, indicating that this is a follow-up of a previously reported SAE and mentioning the date of the original report. Each recurrence, complication, or progression of the original event must be reported as a follow-up to that event, regardless of when it occurs. Follow-up information must describe whether the event resolved or continues, whether and how it was treated, whether there was unblinding or not, and whether the patient continued or discontinued his/her participation in the study.

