# 10 Statistic methods and data analysis

The following sections describe the analyses to be performed.

For the Main Phase of the study, efficacy and safety analyses will be performed with the data collected when all patients enrolled complete their EOS visit. All Follow-up Visit safety data from patients who do not enter the Extension Study will also be included in the safety analyses of the Main Study. A final analysis will be performed when all Extension patients complete their last visit and will be reported either as an additional clinical study report or as an amendment to the Main Phase report. The other additional data at the end of the main study will be analyzed and summarized later in an additional clinical trial report or in a main study report.

Novartis or the designated CRO will analyze all data using the SAS System for data analysis V8.0 or higher. Any data analysis performed independently by an investigator must be submitted to Novartis before its publication or presentation.

Data from all participating sites in this study will be pooled so the appropriate number of patients is available for analysis. The statistical analysis methods described in this section will focus on the data analysis in the main study. Similar methods will be used in the analyses during the extension phase, as appropriate.

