For the Core Period of the study, efficacy and safety analyses will be conducted on the data collected by the time when all the enrolled patients have completed their EOS Visit. All the formal safety follow-up data of those patients who did not enter the extension study will also be included in the core study safety analyses. A final analysis will be completed when all the patients in the Extension complete their last visit and will be reported in either an additional clinical study report or in an addendum to the core study report.

Other additional data prior to the end of the Core Phase of the trial will be analyzed and then summarized in an additional report of clinical study or in a major study report.

Novartis or designated CRO will analyze all data using the SAS System for data analysis 9.4 . Any data analyses carried out independently by an investigator should be submitted to Novartis before publication or presentation.

The data from all centers participating in the trial will be combined, so that an adequate number of patients will be available for analysis. The statistical analysis methods described in this section will focus on the analysis of the data in the core study. Similar methods will be applied to the analyses in the Extension Phase as appropriate.

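### Core adverse-event shells stop at 28 days after the last injection, although the SAP puts the 56-day follow-up of patients not entering the extension into the core safety analyses

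*SAP*

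**What the plan says.** **Length of follow-up.** Protocol 6.4 (Safety Follow-up): "All patients in the main and extension phases will be followed for safety for approximately 56" days, plus or minus 3, after the last dose. Protocol 6.4.1: "All patients will be followed up for AEs and serious adverse events (SAEs) for 8 weeks after administration of the last dose of pasireotide LAR". Protocol 8.1 requires that serious events "up to 56 days after the patient receives the last IM LAR injection of the study drug must be reported to Novartis within 24 hours".

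**What enters the core analysis.** SAP section 5 says that the "formal safety follow-up data of those patients who did not enter the extension study will also be included in the core study safety analyses". Protocol section 10 says the same of Follow-up Visit data: "safety data from patients who do not enter the Extension Study will also be included in the safety analyses of the Main Study". SAP 5.5.3.1 adds: "All AEs recorded during the study will be summarized". SAP 5.5.4 promises counts and percentages of drug-related events in the safety population and sets no time limit.

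**The treatment-emergent window.** SAP 5.5.3.1: "Treatment-emergent adverse events (TEAEs) will include all adverse events who started between first and 28 days after the last administration of study medication". SAP section 7 declares this definition as a clarification to the protocol. Protocol 10.5.3.1 uses the term treatment-emergent without giving an end date.

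**Serious events.** SAP 5.5.3.1 says that deaths and "non-fatal serious adverse events will be listed by patient and tabulated by type of AE", with no reference to the window.

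**The shells.** SAP section 6 refers the core results to Appendix 1. Every adverse-event shell there, Tables 15 to 23, carries treatment-emergent in its title. Tables 32 (vital signs) and 33 (physical examination, including weight) have columns V1 to V10 only. SAP Table A 1 marks both vital signs and weight at Visit 11, and SAP 5.5.3.3 promises summaries of both at each time point.

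**The concern.** A programmer who builds the core tables from Appendix 1 would apply the 28-day filter to all nine adverse-event tables. For a patient who does not enter the extension, an event starting after that cutoff would meet the SAP's promise that all recorded events are summarized and that the follow-up is included, yet would have no table to appear in. The extension shells B 9 to B 17 cannot take it, because they are titled for the extension study.

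Overall safety and tolerability is a stated secondary objective. Protocol 6.4.4 gives patients who stop early the same visits at 28 and 56 days after the last dose, so those who stop because of an adverse event are among those affected. The drug is a depot: Protocol 1.2 reports simulated steady-state residual concentrations of 5.5 and 11.5 ng/mL at 40 and 60 mg, from healthy-volunteer data with dosing every 28 days. Events in the second four weeks are therefore of some interest, whether or not they are labelled treatment-emergent.

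**Working it through.** **Inputs.**
- Main Phase injections on Day 0 and Weeks 4, 8, 12, 16 and 20 (Protocol 7.3).
- Visit 10 on Day 168 and Visit 11 on Day 196 (Protocol Table 7-1, SAP Table A 1).
- Treatment-emergent window: 28 days after the last administration (SAP 5.5.3.1).
- Follow-up: 56 days after the last dose (Protocol 6.4 and 6.4.1).
- Planned enrolment 23, with 19 evaluable (SAP 5.6).

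**Reproducing the schedule.**
- Last Main Phase injection: 5 × 28 = Day 140.
- Follow-up visit: 140 + 56 = Day 196, which matches Visit 11.
- Extension check: last injection Day 644; 644 + 56 = Day 700, which matches Visit 29.

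**Applying the window.**
- Window closes: 140 + 28 = Day 168, the planned day of Visit 10.
- Uncovered: Days 169 to 196, i.e. 196 − 168 = 28 days.
- Share of the post-dose follow-up: 28/56 = 50%. Share of the whole 196 days: 28/196 = 14.3%.
- With the ± 3 day allowance, Visit 10 falls on post-dose days 25 to 31 and Visit 11 on days 53 to 59, so essentially the whole Visit 10 to Visit 11 interval lies outside the window. Early discontinuers have the same offsets.

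**Size across patients.** The documents do not say how many patients will decline or be unable to enter the extension. Let n be that number, each with full follow-up; uncovered time = 28 × n patient-days.

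| n (assumed) | Uncovered patient-days |
|---|---|
| 0 | 0 |
| 4 (= 23 − 19) | 112 |
| 5 | 140 |
| 10 | 280 |
| 23 (nobody enters) | 644 |

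No event rate is given, so this is observation time and not a number of lost events.

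**Text against core shells.**

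| Item | Text | Core shell |
|---|---|---|
| All recorded events | Summarized (SAP 5.5.3.1) | None outside the treatment-emergent titles |
| Drug-related events | Counted, no window (SAP 5.5.4) | Tables 18, 19, 22, 23: treatment-emergent |
| Deaths and serious events | Listed and tabulated, no window (SAP 5.5.3.1) | Tables 17, 19, 21, 23: treatment-emergent; the title of Table 15 may leave serious events unrestricted |
| Vital signs, weight | Each time point (SAP 5.5.3.3); marked at Visit 11 (Table A 1) | Tables 32, 33 end at V10 |
| Physical examination, ECOG | Abnormalities identified and listed only (SAP 5.5.3.3) | Tables 33, 34 end at V10; no by-visit table is promised |

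The adverse-event row of SAP Table A 1 has no mark at Visit 11. Protocol section 4 evaluates potential events on all visits, Protocol 7.5.1 requires questioning at every visit, and Protocol 6.4.1 follows events for 8 weeks. The 4-week figure in Protocol 7.5.1 is a minimum and is compatible with 8 weeks. Only the missing schedule mark needs reconciling, and it may be an artefact of how the table was read from PDF.

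**The case against.** The strongest reply is that the governing text already covers the late events. It says that all recorded events are summarized, it includes the follow-up data, and no sentence excludes days 29 to 56. The shells are also loose in general: V401 is scheduled for vital signs, weight, PT and liver tests but has no column in Tables 25, 28, 32 or 33; Table 24 has V2, V3 and V6 columns where no hematology is scheduled; the laboratory shift tables promised in SAP 5.5.3.2 have no shell; and Tables B 12 and B 13 share one title although their rows differ. Inside Tables 15 to 23 the row labels say only adverse events, so it is the titles that restrict them.

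Most of this stands. It rules out reading Appendix 1 as a deliberate decision to leave the follow-up out. It does not remove the need for a correction: SAP section 6 names Appendix 1 as the place for the core results, and all nine titles point the same way.

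A reader might also infer that the 56-day period is reported for the extension but not for the core. For adverse events the documents do not support this. Tables B 9 to B 17 state no window, and SAP section 5 applies similar methods to the extension. The V29 columns in B 24 to B 26 concern vital signs, physical examination with weight, and ECOG status only.

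**Conclusion.** The inconsistency is real and confined to core safety reporting. If Appendix 1 is followed as written, onsets on days 29 to 56 after the last injection in patients not entering the extension have no core table, and Visit 11 vital signs and weight have no column. The adverse-event gap is mainly for non-serious events, since the text separately promises that deaths and serious events will be listed and tabulated. The uncovered period is 28 days per affected patient. The total depends on an unstated number of patients, and the event count is unknown. The primary efficacy analysis is not affected.

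Three stronger readings should be resisted. A missing shell does not show that the events will be omitted. The 28-day definition is declared in SAP section 7 and is consistent with the protocol's 4-week minimum, so it is not an error. Physical examination and ECOG at Visit 11 are not owed a by-visit table, because SAP 5.5.3.3 promises only that abnormalities be identified and listed.

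**What to change.** - Keep the 28-day treatment-emergent definition and Tables 15 to 23.
- Add core tables of all adverse events, all serious events and all drug-related events, showing onsets on days 29 to 56 after the last injection separately for patients who do not enter the extension.
- Add a Visit 11 column for vital signs and weight in Tables 32 and 33. Columns for physical examination (Table 33) and ECOG (Table 34) are optional.
- Reconcile the missing Visit 11 mark in the adverse-event row of the schedule with Protocol section 4, 6.4.1 and 7.5.1, so that it is plain that events are recorded through the follow-up visit.

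The cost is a few added shells, a column in two or three tables, and one schedule clarification. Reported event counts in the all-event tables will be slightly higher than in the treatment-emergent tables. Making the change before programming avoids a later deviation, which SAP section 7 would require the sponsor to accept in advance and the analysis report to document.

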5.5.3.3 Other safety data

Weight, height and vital signs will be summarized at each time point using descriptive statistics (N, mean, standard-deviation, median, minimum, and maximum).

Abnormalities of physical examination, ECOG performance status, radiological examinations, ECG, MRI, and visual evaluations will be identified and listed.

5.5.4 Tolerability

Dose reductions and AEs related to study drug e.g. gastrointestinal disorders, glucose metabolism disorders, cardiac functions disorders, laboratory abnormalities, infections, injection site reactions will be summarized by presenting counts and percentages for the safety population.

5.6 SAMPLE SIZE RATIONAL

This is a proof of concept study. The sample size of 19 evaluable patients was selected without regard for statistical power. A response rate (proportion of patients with tumor volume reduction ≥ 20%) of at least 10% is considered clinically meaningful for this patient population. **Table A 3**, presents for various assumed response rates the probability of having two or more responders. If the true response rate is 10%, the probability of getting two or more responders out of 19 patients is 58%. In this trial the 90% CI will also be obtained. **Table A 4**, presents the exact 90% CI when 2-6 patients respond out of the 19 patients. Considering the dropout of 20%, we will enrol 23 patients to get 19 evaluable patients for final analysis.

Table A 3: Probability of getting ≥ 2 response in a sample of 19 patients

Assumed p	0.05	0.10	0.15	0.20	0.25	0.30
P(X ≥ 2)	25%	58%	80%	92%	97%	99%
X is assumed to have	binomial distri	bution with	probability	р		

Table A 4: Resulting 90% CIs for various number of observed responders

Responders/n	Lower confidence limit	Upper confidence limitl
2/19	1.9%	29.6%
3/19	4.4%	35.9%
4/19	7.5%	41.9%
5/19	11%	47.6%
6/19	14.7%	53%

6 Study Results

The study results are presented in Appendix 1: Statistical Tables – Core study phase.

The extension study results are presented in Appendix 2: Statistical Tables – Extension study.

7 Clarifications to the study protocol

The following clarifications to the study protocol were considered on this SAP:

- Clarification of statistical analysis for time to response and baseline characteristics
- Definition of treatment-emergent adverse events
- Definition of comparative analysis of hormonal parameters
- Confidence interval of 95% instead of 90% due to the standard approach in clinical epidemiology

Any deviations from methodology/definitions/analysis described on this SAP should be previously accepted by the sponsor and documented (together with reasoning, if relevant) in the statistical analysis report.

Appendix 1: Statistical Tables - Core study phase

Table 1 – Patients' disposition

Total (n=xx) Patients eligible for study treatment, n (%) Inclusion criteria Exclusion criteria Other Total Treatment duration completed as per protocol, n (%) Yes No Total Primary reason for end of treatment, n (%) Adverse Event(s) Subject withdrew consent Lost to follow-up Administrative problems. Death Disease progression Subject is unable to tolerate the minimum pasireotide LAR dose of 40 mg. Acute or progressive vision loss confirmed by a new visual field evaluation. Uncontrolled diabetes mellitus. Clinically significant abnormal test procedure result(s). Clinically significant abnormal laboratory value(s) Protocol deviation Investigator's decision Other Study populations, n (%) FAS Safety

Table 2 – Demographics – FAS population

Table 2 – Demographics – FAS population	
	Total
	(n=xx)
Gender, n (%)	
Male	
Female	
Childbearing potential	
Non-childbearing potential	
Total	
Age (years)	
N	
Mean	
Median	
Standard Deviation	
Minimum	
Maximum	
Race, n (%)	
White / Caucasian ancestry	
Black/ / African ancestry	
Native ancestry	
Asian ancestry	
Other	
Total	
Height (cm)	
N	
Mean	
Median	
Standard Deviation	
Minimum	
Maximum	
Weight (kg)	
N	
Mean	
Median	
Standard Deviation	
Minimum	
Maximum	
BMI (Kg/m²)	
N N	
Mean	
Median	
Standard Deviation	
Minimum	
Maximum	
THE ANTIQUE	

Table 3 – Medical history – FAS population

Table 3 – Medical history – FAS population		
	Total	
	(n=xx)	
Duration of disease (years) ^{a)}		
N		
Mean		
Median		
Standard Deviation		
Minimum		
Maximum		
Medical history or current medical condition prior	to first	
study drug administration, n (%)		
Yes		
No		
Total		

a) The difference between the initial visit and the date of diagnosis of pituitary adenocarcinoma, in years.

Table 4 – Concomitant medication

	Total	
	(n=xx)	
Any medication or significant non	-drug therapy, n (%)	
Yes		
No		
Total		
Concomitant medication for horn	one replacement, n (%)	
Yes		
No		
Total		

Table 5 – HbA1c, fasting blood insulin and glucose at visit 1 – FAS population

Total (n=xx) HbA1c performed, n (%) Yes No Total HbA1c (%) Ν Mean Median Standard Deviation Minimum Maximum Normal Abnormal Clinically significant Non-clinically significant HbA1c ≤7% Yes No Total Fasting blood insulin (ulU/mL), n (%) Yes No Total Fasting blood insulin (ulU/mL) Mean Median **Standard Deviation** Minimum Maximum Normal Abnormal Clinically significant Non-clinically significant Fasting blood glucose (mg/dL), n (%) Yes No Total Fasting blood glucose (mg/dL) Mean Median Standard Deviation Minimum Maximum Normal Abnormal Clinically significant Non-clinically significant

Table 6 – Treatment – FAS population

	Tota (n=x															
		/2		V4		V5		V7		V8		V9		V10		ore nase
Study medication																
administered, n																
(%)																
Yes															-	-
No															-	-
Total															-	-
Dose, n (%) 60 mg															_	_
40 mg Total															-	-
Dose																
adjustment, n (%)																
Yes																
	-	-	-	-	-	-	-	-	-	-	-	-	-	-		
No Total	-	-	-	-	-	-	-	-	-	-	-	-	-	-		
Exposure																
(days) ^{a)}																
N	-	-	-	-	-	-	-	-	-	-	-	-	-	-		
Mean	-	-	-	-	-	-	-	-	-	-	-	-	_	-		
Median	-	-	-	-	-	-	-	-	-	-	-	-	_	-		
Standard	-	-	-	-	-	-	-	-	-	-	-	-	-	-		
Minimum	-	-	-	-	-	-	_	-	_	-	_	-	_	-		
Maximum	-	-	-	-	-	-	-	-	-	-	-	-	-	-		
Mean																
administration dose (mg)b)																
N	_	-	_	_	_	_	_	_	_	_	_	_	_	_		
Mean	-	-	-	-	-	-	-	-	-	-	-	-	-	-		
Median	-	-	-	-	-	-	-	-	-	-	-	-	-	-		
Standard	-	-	-	-	-	-	-	-	-	-	-	-	-	-		
Minimum	_	_	_	-	_	-	_	_	_	-	_	_	_	-		
Maximum	-	-	-	-	-	-	-	-	-	-	-	-	-	-		
Dose reduction																
before tumor volume																
reduction of at																
least 20%																
No																
Total																

a) The difference between the last administration and the first administration, in days.

b) Cumulative dose (total dose administered) divided by number administrations.

Table 7 – Magnetic resonance imaging – FAS population

	Total (n=xx)						
	V1	V4	95%CI	V7	95%CI	V10	95%CI
Volume (cm³)							
N			-		-		-
Mean			-		-		-
Median			-		-		-
Standard			-		_		_
Minimum			_		_		_
Maximum							
Tumor is not			_		_		_
Missing values			-		-		-
Volume change ^{a)}							
(cm³)							
N	-						
Mean	-						
Median	-						
Standard	-						
Minimum	-						
Maximum	-						
Percentage							
change in							
volume ^{a)} (%)							
N	-						
Mean	_						
Median	_						
Standard	_						
Minimum	_						
Maximum	-						
Reduction of							
tumor							
volume ^{b)} , n (%)							
Yes							
No							
≥20% tumor							
volume							
reduction ^{c)} , n							
(%)							
Yes							
No			-		-		-
Total			-		-		-
≥20% tumor							
volume							
reduction using							
LOCF method, n							
(%)							
Yes			-		-		
No			-		-		
Total							

95%CI: 95% confidence interval.

a) The difference between visit i and V1.

b) For reduction='yes' will be considered all patients who obtained 'volume in visit i – volume in V1' >0.
c) For reduction ≥20%='yes' will be considered all patients who obtained 'Percentage change in volume at visit i' ≥20.

Table 8 – Time to response – FAS population

	Total		
	(n=xx)		
	Statistics	95% CI	
Time to response			
N			
Censored			
Events (Reduction ≥20% in tumor volume)			
Mean			
Median			
25 th Percentile			
75 th Percentile			
Range			

Cl_{95%}: 95% confidence interval.

Time between first administration and first date of reduction ≥20% in tumor volume.

Figure 3 – Kaplan-Meier curve for time to response – FAS population

Table 9 – Time to response versus baseline characteristics – FAS population

Time to response a)	Total					
	n=(xx) Statistics	Cl _{95%}	Statistics	Cl _{95%}		
	Statistics	C13576	Statistics	G19376		
Visual field at baseline	Normal		Abnormal			
Fime to response ^{a)}						
N						
Censored						
Events (progression or death)						
Mean						
Median						
25 th Percentile						
75 th Percentile						
Range						
Hazard ratio ^{b)}						
p-value						
Dose at V2	60 mg		40mg			
Time to response a)	oo mg		TVIIIS			
N						
Censored						
Events (progression or death)						
Mean						
Median						
25 th Percentile						
75 th Percentile						
Range						
Hazard ratio b)						
p-value						
•						
Dose reduction before response	Yes		No			
Time to response a)						
Time to response ^{a)} N Censored						
Time to response ^{a)} N						
Time to response ^{a)} N Censored Events (progression or death) Mean						
N Censored Events (progression or death) Mean Median						
N Censored Events (progression or death) Mean Median 25 th Percentile						
N Censored Events (progression or death) Mean Median 25 th Percentile 75 th Percentile						
N Censored Events (progression or death) Mean Median 25 th Percentile						
N Censored Events (progression or death) Mean Median 25 th Percentile 75 th Percentile						
N Censored Events (progression or death) Mean Median 25 th Percentile 75 th Percentile Range						
N Censored Events (progression or death) Mean Median 25 th Percentile 75 th Percentile Range Hazard ratio ^{b)} p-value						
N Censored Events (progression or death) Mean Median 25 th Percentile 75 th Percentile Range Hazard ratio ^{b)} p-value						
Time to response a) N Censored Events (progression or death) Mean Median 25 th Percentile 75 th Percentile Range Hazard ratio b) p-value Duration of disease (years)						
N Censored Events (progression or death) Mean Median 25 th Percentile 75 th Percentile Range Hazard ratio ^{b)} p-value Duration of disease (years) Hazard ratio ^{b)}						
N Censored Events (progression or death) Mean Median 25 th Percentile 75 th Percentile Range Hazard ratio ^{b)} p-value Duration of disease (years) Hazard ratio ^{b)}						
Time to response a) N Censored Events (progression or death) Mean Median 25 th Percentile 75 th Percentile Range Hazard ratio b) p-value Duration of disease (years) Hazard ratio b)						
Time to response a) N Censored Events (progression or death) Mean Median 25 th Percentile 75 th Percentile Range Hazard ratio b) p-value Duration of disease (years) Hazard ratio b) p-value						
Time to response a) N Censored Events (progression or death) Mean Median 25 th Percentile 75 th Percentile Range Hazard ratio b) p-value Duration of disease (years) Hazard ratio b)						

Cl_{95%}: 95% confidence interval.

Time between first administration and first date of reduction ≥20% in tumor volume.

a) Kaplan-Meier estimates. b) Cox regression estimates.

Table 10 – Disease-related symptoms – FAS population

	Total									
	(n=xx) V1	V2	V3	V4	V5	V6	V7	V8	V9	V10
Headache ^{a)} , n (%)										
Absent										
Mild										
Moderate										
Severe										
Very severe										
Total										
Improved, n (%)										
Yes										
95%CI										
No										
Total										
Visual disturbances a),	n									
(%)										
Absent										
Mild										
Moderate										
Severe										
Very severe										
Total										
Total										
Improved, n (%)										
Yes										
95%CI										
No										
Total										

Table 10 (Cont.) – Disease-related symptoms – FAS population

	Total									
	(n=xx)									
	V1	V2	V3	V4	V5	V6	V7	V8	V9	V10
Fatigue ^{a)} , n (%)										
Absent										
Mild										
Moderate										
Severe										
Very severe										
Total										
Improved, n (%)										
Yes										
95%CI										
No										
Total										
Erectile dysfunction	1 b)									
n(%)	. ,									
Yes										
No										
Total										
Improved, n (%)										
Yes										
95%CI										
No										
Total										

Table 10 (Cont.) – Disease-related symptoms – FAS population

	Total (n=xx)									
	V1	V2	V3	V4	V5	V6	V7	V8	V9	V10
Regular menses ^{c)} ,	n									
(%)										
Yes										
No										
Total										
mproved, n (%)										
Yes										
95%CI										
No										
Total										

a) For each symptom, it will considered as improvement if the severity reduce at least one point (eg. 'Severe' at v₁ and 'moderate' at v₁ will be considered as improvement in vi).

b) For patients who registered 'No' in V₁ and 'Yes' in v_i it will be considered as an improvement in v_i.

c) For patients who registered 'No' in V₁ and 'Yes' in v_i it will be considered as an improvement in v_i.

Table 11 (Cont.) – Alpha-subunit – FAS population

	Total (n=xx)					
	V1	V4	V7	95%CI	V10	95%CI
α subunit (ng/mL)						
N				-		-
Mean				-		-
Median				-		-
Standard Deviation				-		-
Minimum				-		-
Maximum				-		-
Normal				-		-
Abnormal				-		-
CS				-		-
NCS				-		-
Reduction of α subunit ≥50% ^{c)} , n (%)						
Yes						
No						
Total						

CS: Clinically significant; NCS: Not clinically significant. 95%CI: 95% confidence interval.

c) For reduction ≥50%='yes' will be considered all patients who obtained percentage change from baseline in α subunit at visit i' ≥50.

Table 13 – Visual field – FAS population

	Total							
	(n=xx)							
	V1	V2	V4	V5	V7	V8	V9	V10
Right eye								
Normal/abnormal, n (%)								
Normal								
Abnormal								
Mild								
Severe								
Total								
Findings, n (%)								
Upper right quadrantanopia								
Upper left quadrantanopia								
Lower right quadrantanopia								
Lower left quadrantanopia								
Temporal hemianopsia								
Nasal hemianopsia								
Other								
Evolutive information, n (%)								
Stable								
Improved								
Worsened								
Total								
Left eye								
Normal/abnormal, n (%)								
Normal								
Abnormal								
Mild								
Severe								
Total								
Findings, n (%)								
Upper right quadrantanopia								
Upper left quadrantanopia								
Lower right quadrantanopia								
Lower left quadrantanopia								
Temporal hemianopsia								
Nasal hemianopsia								
Other								

Table 13 (Cont.) – Visual field – FAS population

	Total (n=xx)							
	V1	V2	V4	V5	V7	V8	V 9	V10
Left eye Evolutive information, n (%) Stable Improved Worsened Total								

Table 14 – Gallblader ultrasound – FAS population

	Total	
	(n=xx) V1	V10
Gallblader ultrasound performed, n	9/1	
Yes	70)	
No		
Total		
If yes		
Any gallstones detected, n (%)		
Yes		
No		
Total		
Dilatation of the intra or extra hep	patic	
ductal system, n (%)		
Yes		
No		
Total		
Location of dilatation, n (%)		
Intrahepatic ductal system		
Extrahepatic ductal system		
Total		

Table 15 – Treatment-emergent adverse events and serious adverse events – Safety population

Total (n=xx) Patients with at least one adverse event, n (%)a) Yes Total Patients with at least one serious adverse event, n (%)a) No Total Grade of adverse events, n (%)b) Grade 1 Grade 2 Grade 3 Grade 4 Total Grade ≥ 3 Relationship of study drug, n (%)b) Not suspected Suspected Total Action taken for adverse event, n (%)b) No action taken. Study drug dosage adjusted / temporarily interrupted. Study drug permanently discontinued due to this adverse event Concomitant medication taken Non-drug therapy given Hospitalization / prolonged hospitalization Serious adverse events, n (%)b) Yes No

a) Percentage calculated within the total number of patients of safety population (n=xx).

b) Percentage calculated within the total number of adverse events reported by safety population (n=xxx).

Table 16 – Incidence of treatment-emergent adverse events – Safety population

	Total
	(n=xx)
Incidence of adverse events, n (%)	
Xxxxx	

a) Percentage calculated for total of patients of patients of the safety population (n=xx).

Table 17 – Incidence of serious treatment-emergent adverse events – Safety population

	Total
	(n=xx)
Incidence of serious adverse events, n (%	
Xxxxx	

a) Percentage calculated for total of patients of patients of the safety population (n=xx).

Table 18 – Incidence of treatment-emergent adverse events with suspected relationship with study drug – Safety population

	Total	
	(n=xx)	
Incidence of adverse events with suspected relationship with study drug, n (%)	у	
Xxxxx		

a) Percentage calculated for total of patients of patients of the safety population (n=xx).

Table 19 – Incidence of serious treatment-emergent adverse events with suspected relationship with study drug – Safety population

	Total	
	(n=xx)	
Incidence of serious adverse events with study drug, n (%)	suspected relationship with	
Xxxxx		

a) Percentage calculated for total of patients of patients of the safety population (n=xx).

Table 20 – Treatment-emergent adverse events – Safety population

	Total (n=xx)	
Adverse events, n (%)		
Xxxxx		

Percentage calculated within the total number of adverse events reported by safety population (n=xxxx).

Table 21 – Serious treatment-emergent adverse events – Safety population

	Total	
	(n=xx)	
Serious adverse events, n (%)		
Xxxxx		

Percentage calculated within the total number of serious adverse events reported by safety population (n=xxxx).

Table 22 – Treatment-emergent adverse events with suspected relationship with study drug – Safety population

	Total	
	(n=xx)	
Adverse events with suspected rela	itionship with study drug, n (%)	
Xxxxx		

Percentage calculated within the total number of adverse events with remote, possible or probable relationship with study drug reported by safety population (n=xxxx).

Table 23 – Serious treatment-emergent adverse events with suspected relationship with study drug – Safety population

	Total	
	(n=xx)	
Serious adverse events with suspected relationship with study d n (%)	rug,	
Xxxxx		
Xxxxx Xxxxx		
Xxxxx		
Xxxxx Xxxxx		

Percentage calculated within the total number of serious adverse events with remote, possible or probable relationship with study drug reported by safety population (n=xxxx).

Table 24 – Hematology – Safety population

	Total (n=xx)									
	V1	V2	V3	V4	V5	V6	V7	V8	V9	V10
RBC count ((millior	/mm³)									
N	•									
Mean										
Median										
Standard										
Minimum										
Maximum										
Normal										
Abnormal										
CS										
NCS										
Hemoglobin (g/dL)										
N										
Mean										
Median										
Standard										
Minimum										
Maximum										
Normal										
Abnormal										
CS										
NCS										
Hematocrit (%)										
N										
Mean										
Modian										
Median Standard										
Minimum										
Maximum										
Normal										
Abnormal										
CS										
NCS										

Table 24 (Cont.) – Hematology – Safety population

i able 24 (Cont.)	Total (n=xx)	• • •								
	V1	V2	V3	V4	V5	V6	V7	V8	V9	V10
WBC count (/mm ³ N Mean Median Standard Minimum	3)									
Maximum Normal Abnormal CS NCS										
Eosinophils (/mm N Mean Median Standard Minimum Maximum	³)									
Normal Abnormal CS NCS										
Neutrophils total N Mean Median Standard Minimum Maximum	(/mm³)									
Normal Abnormal CS NCS	ut: NCS: Not clinically									

Table 24 (Cont.) – Hematology – Safety population

	Total (n=xx)									
	V1	V2	V3	V4	V5	V6	V7	V8	V9	V10
Lymphocytes (/n N Mean Median Standard Minimum Maximum	nm³)									
Normal Abnormal CS NCS										
Monocytes (/mn N Mean Median Standard Minimum Maximum	n³)									
Normal Abnormal CS NCS										
Basophils (/mm³ N Mean Median Standard Minimum Maximum)									
Normal Abnormal CS NCS	ınt: NCS: Not clinically	olon Wisson b								

Table 24 (Cont.) – Hematology – Safety population

	Total (n=xx)									
	V1	V2	V3	V4	V5	V6	V7	V8	V9	V10
Band neutrophils	s (/mm³)									
N	. ,									
Mean										
Median										
Standard										
Minimum										
Maximum										
Normal										
Abnormal										
CS										
NCS										
Distalst	· · - a - a - d / · · - 3\									
Platelet count (tl	nousana/mm³)									
N										
Mean Median										
Standard										
Minimum										
Maximum										
Normal										
Abnormal										
CS NCS										

Table 25 – Coagulation – Safety population

	Total						
	(n=xx)						
	V1	V2	V3	V4	V5	V6	V10
PT (%) N Mean Median Standard Deviation Minimum Maximum							
Normal Abnormal CS NCS							
PT (seconds) N Mean Median Standard Deviation Minimum Maximum			- - - - -	- - - -	- - - - -		
Normal Abnormal CS NCS			- - - -	- - -	- - - -		

Table 25 (Cont.) - Coagulation – Safety population

	Total (n=xx)						
	V1	V2	V3	V4	V5	V6	V10
APTT (%) N Mean Median Standard Deviation Minimum Maximum							
Normal Abnormal CS NCS							
APTT (seconds) N Mean Median Standard Deviation Minimum Maximum			- - - -	- - - -	- - - -		
Normal Abnormal CS NCS			- - -	- - - -	- - -		

Table 26 – Urinalysis – Safety population

	Total						
	(n=xx) V1	V4	V5	V7	V8	V9	V10
Specific gravity							
N Mean Median Standard Deviation Minimum Maximum							
Normal Abnormal CS NCS							
PH N Mean Median Standard Deviation Minimum Maximum							
Normal Abnormal CS NCS							
Glucose, n (%) Negative 100 mg/dl or 5 mmol/L 250 (+)mg/dl or 15 mmol/L 500 (++)mg/dl or 30 mmol/L 1000 (+++)mg/dl or 60 mmol/L 2000 (++++) mg/dL or 110 mmol/L Total							
Normal Abnormal CS NCS St Clinically significant: NCS: Not clinically							

Table 26 (Cont.) – Urinalysis – Safety population

	Total (n=xx)						
	V1	V4	V5	V7	V8	V9	V10
Protein, n (%) Negative Trace 30 (+)mg/dl or 0.3 g/L 100 (++)mg/dl or 1.0 g/L 300 (+++)mg/dl or 3.0 g/L > 2000 (++++) mg/dL or > 20 g/L Total							
Normal Abnormal CS NCS							
